12.2.4 Response Criteria for Patients with Solid Tumor and Measurable Disease

12.2.4.1 **Evaluation of Target Lesions**

Complete Response (CR):	Disappearance of all target and non-target lesions. Any pathological lymph nodes (whether target or non-target) must have reduction in short axis to <10 mm. If immunocytology is available, no disease must be detected by that methodology. Normalization of urinary catecholamines or other tumor markers if elevated at study enrollment (for patients with neuroblastoma).
Partial Response (PR):	At least a 30% decrease in the sum of the diameters of target lesions, taking as reference the baseline sum diameters
Progressive Disease (PD):	At least a 20% increase in the sum of the diameters of target lesions, taking as reference the smallest sum on study (this includes the baseline sum if that is the smallest on study). In addition to the relative increase of 20%, the sum must also demonstrate an absolute increase of at least 5 mm. (Note: the appearance of one or more new lesions is also considered progressions). Note: in presence of SD or PR in target disease but unequivocal progression in non-target or non-measurable disease, the patient has PD if there is an overall level of substantial worsening in non-target disease such that the overall tumor burden has increased sufficiently to merit discontinuation of therapy
Stable Disease (SD):	Neither sufficient shrinkage to qualify for PR nor sufficient increase to qualify for PD, taking as

reference the smallest sum diameters while on study

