12.5.1 Measurable Disease

Any lesion that is at minimum 10 mm in one dimension on standard MRI or CT, for CNS tumors.

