12.5.3 Selection of Target and Non-Target Lesions

For most CNS tumors, only one lesion/mass is present and therefore is considered a “target” for measurement/follow up to assess for tumor progression/response. If multiple measurable lesions are present, up to 5 should be selected as “target” lesions. Target lesions should be selected on the basis of size and suitability for accurate repeated measurements. All other lesions will be followed as non-target lesions. The lower size limit of the target lesion(s) should be at least twice the thickness of the slices showing the tumor to decrease the partial volume effect (e.g., 8 mm lesion for a 4 mm slice).

Any change in size of non-target lesions should be noted, though does not need to be measured.

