12.5.4 Response Criteria for Target Lesions

Response criteria are assessed based on the product of the longest diameter and its longest perpendicular diameter. Development of new disease or progression in any established lesions is considered progressive disease, regardless of response in other lesions – e.g., when multiple lesions show opposite responses, the progressive disease takes precedence. Response Criteria for target lesions:

- **Complete Response (CR)**: Disappearance of all target lesions.
- **Partial response (PR)**: $\geq 50\%$ decrease in the sum of the products of the two perpendicular diameters of all target lesions (up to 5), taking as reference the initial baseline measurements.
- **Stable Disease (SD)**: Neither sufficient decrease in the sum of the products of the two perpendicular diameters of all target lesions to qualify for PR, nor sufficient increase in a single target lesion to qualify for PD.
- **Progressive Disease (PD)**: 25% or more increase in the sum of the products of the perpendicular diameters of the target lesions, taking as reference the smallest sum of the products observed since the start of treatment, or the appearance of one or more new lesions.

12.5.5 Response Criteria for Non-Target Lesions:

- **Complete Response (CR)**: Disappearance of all non-target lesions.
- **Incomplete Response/Stable Disease (IR/SD)**: The persistence of one or more non-target lesions.
- **Progressive Disease (PD)**: The appearance of one or more new lesions and/or unequivocal progression of existing non-target lesions.

12.5.6 Response criteria for tumor markers (if available):

Tumor markers will be classified simply as being at normal levels or at abnormally high levels.

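### CNS measurability has a size floor on one diameter, but response is scored on the product of two, so a 1 mm change in a thin lesion can count as progression

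*Combined protocol and SAP*

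**What the plan says.** All references are to the combined protocol and SAP.

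- **Size floor (12.5.1).** Measurable CNS disease is "Any lesion that is at minimum 10 mm in one dimension on standard MRI or CT, for CNS tumors". No minimum is given for the perpendicular diameter.
- **Metric (12.5.4).** "Response criteria are assessed based on the product of the longest diameter and its longest perpendicular diameter".
- **PD threshold (12.5.4).** PD is defined as "25% or more increase in the sum of the products of the perpendicular diameters of the target lesions". The same bullet makes the nadir, not baseline, the comparison point: "taking as reference the smallest sum of the products observed since the start of treatment". No absolute minimum increase and no confirmation of PD is required.
- **Number of lesions (12.5.3).** "For most CNS tumors, only one lesion/mass is present", so the sum is usually a single product.
- **Slice limit (12.5.3).** "The lower size limit of the target lesion(s) should be at least twice the thickness of the slices showing the tumor", illustrated by "e.g., 8 mm lesion for a 4 mm slice". The text does not say which diameter this limits. Targets are also to be chosen for size and for how reliably they can be re-measured.
- **Non-CNS solid tumors (12.2.4.1).** Besides a 20% rise in the sum of diameters, PD has a second condition: "the sum must also demonstrate an absolute increase of at least 5 mm". Section 12.5 has no counterpart.
- **Consequences.** Radiographic PD is a ground for removal from protocol therapy (10.1a), and a further cycle requires no worse than stable disease (5.2). Central review (8.2.1) is named for CR, PR and long-term stable disease, not for PD.

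**The concern.** A size floor is there to keep ordinary measurement differences from crossing a response threshold. Here the floor covers only one of the two numbers that are multiplied together. When the other number is small, a fixed 1 mm difference is a large proportion of the product. A lesion read as 10 x 4 mm at one scan and 10 x 5 mm at the next goes from 40 to 50 mm², which is exactly 25% and therefore PD.

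If that difference is reading variation rather than growth, the patient can come off therapy without true progression. Under Table 3 in 12.6, stable disease or a response followed by progression is recorded as a best response of PD, so the same reading also fixes the patient's entry for secondary aim 1.2.1. With usually one lesion, nothing dilutes the error. With several, the opening of 12.5.4 makes progression in any established lesion count as PD.

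**Working it through.** The plan gives no figure of its own here, so the check is direct arithmetic on the 12.5.4 rule.

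**Inputs.** Long diameter 10 mm (the 12.5.1 floor); short diameter d mm (no floor stated); one target lesion (12.5.3); PD at a relative increase of 25% or more (12.5.4).

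**Formulas.**
- +1 mm on the short diameter only: 10(d+1)/(10d) − 1 = 1/d. This is at least 0.25 when d ≤ 4.
- +1 mm on the long diameter only: 11d/(10d) − 1 = 10% for every d, never PD.
- +1 mm on both: 11(d+1)/(10d) − 1. This is at least 0.25 when 11d + 11 ≥ 12.5d, so d ≤ 11/1.5 = 7.33.

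| Lesion (mm) | +1 mm, short only | +1 mm, both |
|---|---|---|
| 10 x 3 | 33.3% PD | 46.7% PD |
| 10 x 4 | 25.0% PD | 37.5% PD |
| 10 x 5 | 20.0% SD | 32.0% PD |
| 10 x 6 | 16.7% SD | 28.3% PD |
| 10 x 7 | 14.3% SD | 25.7% PD |
| 10 x 8 | 12.5% SD | 23.8% SD |
| 10 x 10 | 10.0% SD | 21.0% SD |

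A 10 x 10 mm lesion needs 10(√1.25 − 1) = 1.18 mm on each diameter to reach PD.

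**If the slice limit did apply to the short diameter.** The floor on d would be twice the slice thickness. The thicknesses below are assumed; 12.5.3 mentions only 4 mm, as an example.
- 2 mm slices: floor 4 mm, 25.0% (short only), PD.
- 3 mm slices: floor 6 mm, 16.7% (short only, SD) and 28.3% (both, PD).
- 4 mm slices: floor 8 mm, 12.5% and 23.8%, no PD.
- 5 mm slices: floor 10 mm, 10.0% and 21.0%, no PD.

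**Measurement from nadir.** A square lesion of side L reaches PD with +1 mm on both when L ≤ 1/(√1.25 − 1) = 8.47 mm. For example, 8 x 8 to 9 x 9 mm is 81/64 − 1 = 26.6%. A lesion that meets any floor at baseline can enter this range after shrinking.

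**False PR.** A 50% fall from 10 x 4 mm needs the short diameter to drop by 2 mm, since (10 x 2)/(10 x 4) = 0.50. A 1 mm drop gives only 25%.

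**Illustration under an assumption not in the documents.** Suppose an unchanged lesion is read at two scans, with independent normal error of SD 0.5 to 1 mm per diameter, rounded to 1 mm. The simulated chance of false PD is 19% to 30% for 10 x 4 mm and 1% to 13% for 10 x 10 mm. A floor on both diameters lowers the risk but does not remove it.

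**The case against.** The strongest case against runs as follows.

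- **Reach.** A reader might infer that 1 mm turns any lesion at the 10 mm floor into PD. The arithmetic does not support this: a change in one diameter needs d of 4 mm or less, and a 10 x 10 mm lesion stays stable at +1 mm on both. The instruction to choose targets that can be re-measured reliably should also screen out some thin lesions. This stands as a limit on the point, although that instruction is qualitative and sets no size.
- **Slice limit.** Read as applying to both diameters, with slices of about 4 mm or more, it would prevent the problem from baseline. The text does not say so, and thinner slices leave the gap open.
- **False PR.** A reader might see an equal risk of spurious response. The documents largely guard against it: 8.1 and 12.2 call for a confirmatory evaluation on the next cycle, Table 3 requires a second assessment, and 8.2.1 sends CR and PR to central review. The 5 mm condition in 12.2.4.1 also applies to PD only, so it offers no contrast for PR. This objection stands.
- **The 8 mm example.** It might be taken as lowering the measurability floor. It more naturally illustrates the slice multiplier for lesions that are already measurable. It is a minor inconsistency.
- **Impact.** A reader might worry about the MTD. That rests on Cycle 1 dose-limiting toxicity (11.2.2), and disease is first scheduled for re-evaluation at the end of Cycle 1 (8.1). Response is secondary and reported descriptively (11.5). This also stands.

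**Conclusion.** The point holds for thin CNS lesions and for lesions that have become small by nadir. On the current text, +1 mm is PD for a 10 x d mm lesion when d ≤ 4 mm (short diameter alone) or d ≤ 7.3 mm (both diameters), measured from baseline. False PD is the error that matters: it leads to removal from therapy, needs no confirmation and is not named for central review.

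What is affected is time on therapy and the descriptive CNS response results, in a trial expecting at most 22 patients in its main scenario (11.1). The MTD rule is not affected. Two things are not in the documents: how often such lesions will enrol, and how large reading error is. The thresholds above need neither, but any statement of how many patients would be misclassified would. This is worth correcting, but it does not undermine the primary aim.

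**What to change.** 1. In 12.5.1 and 12.5.3, apply the existing 10 mm floor and the twice-slice-thickness limit to both perpendicular diameters of a CNS target lesion. Remove or correct the 8 mm example.
2. Make the matching edits so that no patient falls between categories. Section 12.5.2 currently excludes any lesion accurately measurable in one dimension, so a 10 x 6 mm lesion would be neither measurable nor evaluable after step 1. It should instead refer to having no lesion that meets 12.5.1. Section 4.1.5 takes its definitions from 12.2 and 12.3 only and should also cite 12.5. The table in 12.5.7 needs rows for patients without target lesions.
3. A baseline floor does not protect after shrinkage, so the sponsor should reconcile the CNS PD definition in 12.5.4 with the absolute-increase safeguard in 12.2.4.1. That safeguard is expressed in millimeters on a sum of diameters and cannot be carried over unchanged to a sum of products. No value is proposed here, because PD also governs removal from therapy.

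The cost is wording in Sections 4.1.5 and 12.5, with no added visits or scans. The downside is that a few CNS patients move from measurable to evaluable disease and can no longer be scored as PR.

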12.5.2 Evaluable Disease

Evaluable disease is defined as at least one lesion, with no lesion that can be accurately measured in at least one dimension. Such lesions may be evaluable by nuclear medicine techniques, immunocytochemistry techniques, tumor markers, CSF cytology, or other reliable measures.

12.5.3 Selection of Target and Non-Target Lesions

For most CNS tumors, only one lesion/mass is present and therefore is considered a “target” for measurement/follow up to assess for tumor progression/response. If multiple measurable lesions are present, up to 5 should be selected as “target” lesions. Target lesions should be selected on the basis of size and suitability for accurate repeated measurements. All other lesions will be followed as non-target lesions. The lower size limit of the target lesion(s) should be at least twice the thickness of the slices showing the tumor to decrease the partial volume effect (e.g., 8 mm lesion for a 4 mm slice).

Any change in size of non-target lesions should be noted, though does not need to be measured.

12.5.4 Response Criteria for Target Lesions

Response criteria are assessed based on the product of the longest diameter and its longest perpendicular diameter. Development of new disease or progression in any established lesions is considered progressive disease, regardless of response in other lesions – e.g., when multiple lesions show opposite responses, the progressive disease takes precedence. Response Criteria for target lesions:

- **Complete Response (CR)**: Disappearance of all target lesions.
- **Partial response (PR)**: $\geq 50\%$ decrease in the sum of the products of the two perpendicular diameters of all target lesions (up to 5), taking as reference the initial baseline measurements.
- **Stable Disease (SD)**: Neither sufficient decrease in the sum of the products of the two perpendicular diameters of all target lesions to qualify for PR, nor sufficient increase in a single target lesion to qualify for PD.
- **Progressive Disease (PD)**: 25% or more increase in the sum of the products of the perpendicular diameters of the target lesions, taking as reference the smallest sum of the products observed since the start of treatment, or the appearance of one or more new lesions.

12.5.5 Response Criteria for Non-Target Lesions:

- **Complete Response (CR)**: Disappearance of all non-target lesions.
- **Incomplete Response/Stable Disease (IR/SD)**: The persistence of one or more non-target lesions.
- **Progressive Disease (PD)**: The appearance of one or more new lesions and/or unequivocal progression of existing non-target lesions.

12.5.6 Response criteria for tumor markers (if available):

Tumor markers will be classified simply as being at normal levels or at abnormally high levels.

12.5.7 Overall Response Assessment

The overall response assessment takes into account response in both target and non-target lesions, the appearance of new lesions and normalization of markers (where applicable), according to the criteria described in the table below. The overall response assessment is shown in the last column, and depends on the assessments of target, non-target, marker and new lesions in the preceding columns.

Target Lesions	Non-target Lesions	Markers	New Lesions	Overall Response
CR	CR	Normal	No	CR
CR	IR/SD	Normal	No	PR
CR	CR, IR/SD	Abnormal	No	PR
PR	CR, IR/SD	Any	No	PR
SD	CR, IR/SD	Any	No	SD
PD	Any	Any	Yes or No	PD
Any	PD	Any	Yes or No	PD
Any	Any	Any	Yes	PD

Each patient will be classified according to his “best response” for the purposes of analysis of treatment effect. Best response is determined as outlined in [Section 12.6](#) from a sequence of overall response assessments.

12.6 Best Response

12.6.1 Evaluation of Best Overall Response

The best overall response is the best response recorded from the start of the treatment until disease progression/recurrence (taking as reference for progressive disease the smallest measurements recorded since the treatment started). The patient's best response assignment will depend on the achievement of both measurement and confirmation criteria.

Table 3. Sequences of overall response assessments with corresponding best response.

1st Assessment	2nd Assessment	Best Response
Progression		Progressive disease
Stable, PR, CR	Progression	Progressive disease
Stable	Stable	Stable
Stable	PR, CR	Stable
Stable	Not done	Not RECIST classifiable
PR	PR	PR
PR	CR	PR
PR, CR	Not done	Not RECIST classifiable
CR	CR	CR

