12.2.5 Overall Response Assessment

Table 1: For Patients with Measurable Disease (i.e., Target Disease)

Target Lesions	Non-Target Lesions	New Lesions	Overall Response	Best Overall Response when Confirmation is Required*
CR	CR	No	CR	≥ 28 days Confirmation
CR	Non-CR/Non-PD	No	PR	≥ 28 days Confirmation
CR	Not evaluated	No	PR	
PR	Non-CR/Non-PD/not evaluated	No	PR	
SD	Non-CR/Non-PD/not evaluated	No	SD	documented at least once ≥ 28 days from baseline
PD	Any	Yes or No	PD	no prior SD, PR or CR
Any	PD**	Yes or No	PD	
Any	Any	Yes	PD	

* See RECIST 1.1 manuscript for further details on what is evidence of a new lesion.
 ** In exceptional circumstances, unequivocal progression in non-target lesions may be accepted as disease progression.
Note: Patients with a global deterioration of health status requiring discontinuation of treatment without objective evidence of disease progression at that time should be reported as “*symptomatic deterioration.*” Every effort should be made to document the objective progression even after discontinuation of treatment.

Table 2: For Patients with Non-Measurable Disease (i.e., Non-Target Disease)

Non-Target Lesions	New Lesions	Overall Response
CR	No	CR
Non-CR/non-PD	No	Non-CR/non-PD*
Not all evaluated	No	not evaluated
Unequivocal PD	Yes or No	PD
Any	Yes	PD
* ‘Non-CR/non-PD’ is preferred over ‘stable disease’ for non-target disease since SD is increasingly used as an endpoint for assessment of efficacy in some trials so to assign this category when no lesions can be measured is not advised		

Table 4: Overall Response for Patients with Neuroblastoma and Measurable Disease

CT/MRI	MIBG	Bone Scan	Bone Marrow	Catechol	Overall
PD	Any	Any	Any	Any	PD
Any	PD	Any	Any	Any	PD
Any	Any	PD	Any	Any	PD
Any	Any	Any	PD	Any	PD
SD	CR/PR/SD	Non-PD	Non-PD	Any	SD
PR	CR/PR	Non-PD	Non-PD	Any	PR
CR/PR	PR	Non-PD	Non-PD	Any	PR
CR	CR	Non-PD	Non-PD	Elevated	PR
CR	CR	CR	CR	Normal	CR

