12.2.6 Overall Best Response Assessment

Each patient will be classified according to his “best response” for the purposes of analysis of treatment effect. Best response is determined as outlined in [Section 12.6](#) from a sequence of overall response assessments.

12.3 **Response Criteria for Patients with Solid Tumors and Evaluable Disease**

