12.6.2 Duration of Response

Duration of overall response: The duration of overall response is measured from the time measurement criteria are met for CR or PR (whichever is first recorded) until the first date that recurrent or progressive disease is objectively documented (taking as reference for progressive disease the smallest measurements recorded since the treatment started).

The duration of overall CR is measured from the time measurement criteria are first met for CR until the first date that progressive disease is objectively documented.

Duration of stable disease: Stable disease is measured from the start of the treatment until the criteria for progression are met, taking as reference the smallest measurements recorded since the treatment started, including the baseline measurements.

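### For solid tumors assessed under Table 1, Tables 1 and 3 give different best responses when stable disease is followed by progression, and neither is said to prevail

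*Combined protocol and SAP*

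**What the plan says.** Two places assign a best overall response to solid-tumor patients with measurable disease.

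- **Section 12.2.5, Table 1.** Its last column is headed "Best Overall Response when Confirmation is Required". SD qualifies when "documented at least once", 28 or more days after baseline. The PD rows carry the condition "no prior SD, PR or CR". CR and PR need confirmation at 28 days or more.
- **Section 12.6.1, Table 3.** This maps a first and a second assessment to a best response. A first assessment of SD, PR or CR followed by progression is PD. SD with no second assessment is "Not RECIST classifiable".

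Two sentences precede Table 3. The first is the definition: "The best overall response is the best response recorded from the start of the treatment until disease progression/recurrence". The second qualifies it: "The patient's best response assignment will depend on the achievement of both measurement and confirmation criteria".

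Section 12.2.6 connects the two places for these patients: "Best response is determined as outlined in" Section 12.6. Measurable neuroblastoma has its own overall-response table (Table 4), which has no best-response column. Sections 12.3.6, 12.4.5 and 12.5.7 send evaluable-only, MIBG-only and CNS patients to Section 12.6 without using Table 1.

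**The concern.** A patient with SD on the first scan and progression on the second is PD under Table 3 and, if the SD scan was late enough, SD under Table 1. Both tables claim the same patient and the same variable, and no rule ranks them.

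Best response is the classification the protocol names for analyzing treatment effect, and it is the output for secondary aim 1.2.1 on antitumor activity. If the choice of table is made once outcomes are known, the reported number of patients with SD becomes discretionary. In a small phase 1 study that is reported descriptively, those counts are the whole result for this aim.

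**Working it through.** The plan gives no figure to reproduce, so the check sets the two tables side by side and then examines the 28-day condition.

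**Step 1. Sequences covered.** Table 3 has 9 rows. Written out by first and second assessment they give 13 sequences, compared below with Table 1's best-response column.

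| Sequence | Table 3 | Table 1 best-response column | Agreement |
|---|---|---|---|
| PD first (1) | PD | PD | yes |
| SD, PD (1) | PD | SD if the SD scan is at 28 days or later; if earlier, no category, but not PD | **no** |
| PR, PD and CR, PD (2) | PD | not PD if an unconfirmed response is prior; not stated | conditional |
| SD, SD (1) | SD | SD | yes |
| SD, PR and SD, CR (2) | SD | SD, given the 28-day condition | yes |
| SD, not done (1) | unclassifiable | SD if the SD scan is at 28 days or later | conditional |
| PR, not done and CR, not done (2) | unclassifiable | no category stated | not counted |
| PR, PR and PR, CR (2) | PR | PR, given 28-day confirmation | yes |
| CR, CR (1) | CR | CR, given 28-day confirmation | yes |

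Total: 1 + 1 + 2 + 1 + 2 + 1 + 2 + 2 + 1 = 13. One sequence conflicts outright (SD, PD) and three conflict conditionally (SD, not done; PR, PD; CR, PD).

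**Step 2. Early SD does not remove the first conflict.** If SD is seen before 28 days, Table 1's SD condition fails. Its PD condition fails too, because there was prior SD. Table 1 therefore never returns the PD that Table 3 returns.

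**Step 3. When the first scan falls.** Inputs: evaluation on Day 28 of a 28-day cycle (Section 5.1), and baseline imaging up to 14 days before therapy starts (Section 8.1).

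- Day 28 is 28 − 1 = 27 days after Day 1.
- Days from baseline: 27 + 0 = 27 up to 27 + 14 = 41.
- If the 72-hour window of Section 8.1, which is attached to the column for later cycles, is *assumed* to apply here as well, the scan falls 28 − 3 = 25 to 28 days after Day 1. That is 25 + 0 = 25 to 28 + 14 = 42 days from baseline.

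Both ranges straddle 28 and lie mostly above it. SD at the end of Cycle 1 will usually meet Table 1's condition, but not always.

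**Step 4. Scale.** The documents give no rate of SD followed by progression, so the number of patients affected cannot be derived. As illustration only: if all 18 patients (12 for dose finding plus 6 for PK, Section 11.1) were assessable under Table 1, each reclassified patient would move the SD proportion by 1/18 = 5.6 percentage points. With 12 it would be 1/12 = 8.3 points.

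**The case against.** The best defense is that Section 12.6 governs. Section 12.2.6 names it as the place where best response is decided, whereas Table 1 sits under overall response assessment. The confirmation sentence in 12.6.1 is not limited to CR and PR, so SD may be meant to need a second assessment. The unclassifiable row for SD with no second scan fits that intent. Read this way, Table 3 is consistent with 12.6.1.

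That argument has force against one inference a reader might draw, namely that the lead sentence of 12.6.1 flatly contradicts Table 3. The lead sentence favors SD, but the sentence after it leaves room for Table 3. It does not rescue the pair of tables. Table 1 has an explicit best-response column, accepts a single SD documentation and bars PD after SD. If Table 3 governs, that column is wrong and needs correcting.

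The effect is also narrow. Long-lasting SD (6 or more cycles, which goes to central review under Section 8.2.1) is repeated SD, and both tables score it SD. Only SD that ends, or is not followed up, by the second assessment is exposed. Section 11.5 makes all these analyses descriptive. This limits the importance but leaves the conflict in place.

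**Conclusion.** As written, the protocol yields two best responses for SD followed by progression in solid-tumor patients assessed under Table 1. This rests on the text alone. The differences for SD with no further scan, and for PR or CR followed by progression, depend on the 28-day timing and on the undefined word prior respectively.

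The consequence is confined to descriptive counts of SD, PD and unclassifiable patients. No MTD, DLT or dose decision uses them, and no change in a rate is claimed.

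A reader might infer more, but the documents do not support it:

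- **That all tumor groups are affected.** CNS, MIBG-only and evaluable-only patients do not use Table 1, and measurable neuroblastoma uses Table 4. For them there is at most the softer tension with the lead sentence.
- **That Table 3 stops at the first two scans and so loses later confirmed responses.** The protocol classifies from a sequence of assessments, and nothing limits that to two.
- **That a patient scored PD also receives a stable-disease duration.** Section 12.6.2 states "Stable disease is measured from the start of the treatment until the criteria for progression are met". That defines how the duration is measured, not who is assigned one.
- **That the absence of rows for PR then SD, CR then SD and CR then PR is a contradiction.** It is missing detail.

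**What to change.** Before best response is tabulated:

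1. Amend Table 3's SD-then-progression and SD-then-not-done entries so that SD seen at least once, 28 or more days after baseline, is best response SD. The amended entries should also state what SD seen only before 28 days becomes, since Table 1 gives it no category.
2. State whether an unconfirmed PR or CR counts as prior for Table 1's PD condition. That settles PR or CR followed by progression.

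If the sponsor intends Table 3 to govern, leave it unchanged. Correct Table 1's best-response column and the lead sentence of Section 12.6.1 to match, so that only one rule remains.

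The cost is a wording amendment, with no added scans, patients or data. Its effect is that some patients move between SD, PD and unclassifiable, which is why it should be settled before the counts are seen.
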